6 TREATMENT PLAN

6.1 Administration Schedule

6.1.1 Group 1

After randomization and the initial two-week CGM assessment, subjects randomized to Group 1 will be initiated on propranolol ER 80 mg daily (before bedtime) for four weeks, and will then stop the intervention.

6.1.2 Group 2

After randomization randomization and the initial two-week CGM assessment, subjects randomized to Group 2 will be initiated on placebo: one capsule daily (before bedtime) for four weeks, and will then stop the intervention.

6.2 Treatment (include name of each treatment as section header)

6.2.1 How Supplied, Stored, Packaged and Labeled

Propranolol ER 80 mg capsules: Over-encapsulated for blinding.

Matching placebo capsules: Capsules identical to the ones used to encapsulate propranolol ER for blinding.

Store at 20° to 25°C (68° to 77°F); excursions permitted to 15° to 30°C (59° to 86°F). [See USP Controlled Room Temperature] Protect from light, moisture, freezing, and excessive heat. Dispense in a tight, light-resistant container as defined in the USP.

6.2.2 Preparation and Administration

Subjects will be given a 4-week supply of blinded study medication at treatment visit 2. Subjects will be asked to return this supply with any unused capsules at the end of the intervention period.

6.2.3 Accountability and Compliance

Subjects will be asked to medication bottles and any unused capsules for reconciliation at the end of the intervention period.

6.3 Duration of Therapy

The standard treatment period for the interventional period (propranolol or placebo) will last 4 weeks (28 days).

Subjects must be withdrawn or discontinued from the clinical trial for the following reasons:

- Subject withdraws consent from participation in the clinical trial. A subject must be removed from the study at his/her own request. At any time during the trial and without providing reasons, a subject may decline to participate further. The subject will not suffer any disadvantage as a result.
- Subject is lost to follow-up despite efforts to contact
- Death

Subjects may be withdrawn or discontinued from the clinical trial for the following reasons:

- The subject is non-compliant with study treatment requirements and/or protocol procedures, including the use of prohibited concomitant medications.
- The occurrence of an AE, laboratory abnormality, or other medical condition or situation such that in the investigator's opinion, continued participation in the study would not be in the best interest of the subject.
- Development of severe hypoglycemia for which subject was required to visit emergency room or to be hospitalized

Discontinued or withdrawn subjects may be replaced on study to ensure completion of five study subjects in each treatment arm.

7 TOXICITIES AND DOSE MODIFICATION

Toxicities will be monitored in each study subject according to the study calendar and Section 9.9, Safety Measurements. Serious Adverse Events and intolerable toxicities determined by the PI to be related to study medication will result in discontinuation of treatment and withdrawal of the subject from the trial, or treatment may be held for one week and resumed if adverse events resolve to a tolerable level as determined by the investigator.

8 STUDY CALENDAR

Period	Screening ¹	Study ²			
		Intervention Phase			
Visit No.		1	2	3	4
Week	-4 to 1	1	3	5	7
Assessments					
Informed consent	X				
Inclusion/Exclusion criteria	X				
Demographics	X				
Vital signs	X		X		X
Physical Examination	X		X ³	X ³	X ³
Hemoglobin A1C	X				
Pregnancy Test	X		X		
ECG	X				
AE Assessment			X	X	X
Concomitant Medications			X		X
Investigational Drug Treatment			X		
Primary Objective Assessment		X ⁴		X ⁴	
Secondary Objective Assessment		X	X		X

ECG, electrocardiogram; AE, adverse event

1. All screening procedures should be completed within 4 weeks of study enrollment, except that an ECG completed within 3 months will be considered as valid. Screening visit and Study Visit 1 may occur on the same day.
2. All visits within the Intervention Phase should occur within ± 3 days of the target dates. Pregnancy test which must be completed within 48 hours before investigational drug treatment starts.
3. Physical exam to be conducted at the discretion of PI/Sub-investigator based on reported adverse events.
4. Two-week assessment with Hypoglycemia Event Reports and continuous glucose monitoring.

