4 STUDY DESIGN

4.1 Description

The current investigation is a phase II pilot clinical trial with randomization and double-blinding design. After recruitment, the subjects will be randomized into two arms (Group 1 or Group 2), and under go a two-week assessment with Hypoglycemia Event Report and continuous glucose monitoring (CGM) with a Dexcom Professional CGM system. The subjects will then to be placed on either propranolol (Group 1) or placebo (Group 2) for a 4-week Intervention. Two weeks after the intervention is initiated, subjects will again be asked to undergo Hypoglycemic Event Report and CGM assessments for another two weeks.

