4.3 Number of Subjects

Twelve patients will be enrolled and treated on this pilot study. We will use the collected information to conduct a power analysis to determine the number of subjects needed for the definitive trial.

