9.10 Efficacy Measurements

9.10.1 Primary Objective Assessment

The primary objective assessment will be done through the determining the total and self-reported hypoglycemic events based on CGM data and hypoglycemia diary, respectively.

A single CGM hypoglycemic episode will be defined by any CGM readings < 70 mg/dL, followed by at least one reading ≥ 70 mg/dL from the Dexcom Professional Mobile CGM system. A subject's self-reported hypoglycemic episode will be defined by a hypoglycemic symptom record on the hypoglycemia diary with a confirmatory glucose value (glucometer value < 70 mg/dL, or CGM glucose value < 70 mg/dL if glucometer value is not available), or an incidental glucometer value < 70 mg/dL if no hypoglycemia symptom develops.

The Hypoglycemia Event Report includes the initial glucometer value and time and treatment time; the first and the most prominent symptom during the hypoglycemia episode; whether the episode requires outside help (severe hypoglycemia).

At the end of each hypoglycemia event report/CGM assessment (i.e., visits 2 and 4), CGM data will be downloaded into a secure system and exported into an Excel format, and Hypoglycemic Event Reports will be collected for analysis.

The primary objective to determine whether propranolol increases the recognition of hypoglycemic events will be determined by an increase in the ratio of self-reported hypoglycemic events over total (i.e. CGM) hypoglycemic events while subjects are in the intervention period treated with propranolol compared to placebo.

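### A fixed 28-day supply leaves no slack for late Visits 3 and 4, so up to 3 of the 14 outcome days can fall after the last capsule

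*Combined protocol and SAP*

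**What the plan says.** Section 6.1 states that Group 1 "will be initiated on propranolol ER 80 mg daily (before bedtime) for four weeks, and will then stop the intervention"; Group 2 takes placebo on the same schedule. Section 6.2.2 adds: "Subjects will be given a 4-week supply of blinded study medication at treatment visit 2". Section 6.3 gives the treatment length as 28 days. No spare capsules are mentioned.

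The study calendar (section 8) places Visits 1 to 4 at weeks 1, 3, 5 and 7. Footnote 4 describes the primary assessment begun at Visits 1 and 3 as "Two-week assessment with Hypoglycemia Event Reports and continuous glucose monitoring". Footnote 2 says: "All visits within the Intervention Phase should occur within ± 3 days of the target dates". It does not say what the target dates are counted from. Section 4.1 is the closest the plan comes to an anchor: "Two weeks after the intervention is initiated, subjects will again be asked to undergo Hypoglycemic Event Report and CGM assessments", for a further two weeks. Section 9.10.1 ends the two assessments at Visits 2 and 4, and sets the primary comparison "while subjects are in the intervention period treated with propranolol compared to placebo".

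No section extends dosing to a late Visit 4, or excludes diary and CGM days that follow the last capsule.

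**The concern.** On target dates the outcome window is drug days 15 to 28 and the last capsule is taken on day 28, so there is no margin. If Visits 3 and 4 both slip, the window moves later and the capsules do not. The extra days are collected and analysed, yet they do not fit the plan's own description of the outcome as measured on treatment.

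Only the propranolol arm loses active drug on those days, so any effect that needs continued dosing is pulled toward zero. Section 4.3 says of the pilot data: "We will use the collected information to conduct a power analysis to determine the number of subjects needed for the definitive trial". A diluted effect would therefore carry into that calculation. Section 6.3 aims for five completers per arm. In an arm of five, one subject with 3 such days accounts for 3/(5 × 14) = 4.3% of the arm's outcome days.

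**Working it through.** **Inputs.** 28 daily capsules from Visit 2 (6.1, 6.2.2, 6.3); 14-day window from Visit 3 (section 8, footnote 4); second assessment two weeks after drug start (4.1); window closes at Visit 4 (9.10.1); each visit within ±3 days (section 8, footnote 2). Assumption: the first capsule is taken on the evening of Visit 2.

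**Set-up.** Call the first dose day 1. Capsules cover days 1 to 28. The Visit 3 target is day 15 and the Visit 4 target is day 29. Let b and c be their offsets, each from −3 to +3. The outcome days run from 15 + b to the earlier of 28 + b (14 days completed) and 28 + c (the day before Visit 4). Hence

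undosed outcome days = max(0, min(b, c)).

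**The plan's own schedule.** b = c = 0 gives days 15 to 28, with 0 undosed days, as intended.

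**Worst case.** b = c = 3 gives days 18 to 31. Days 29, 30 and 31 have no capsule: 3/14 = 21%. Visit 2 is on time, the baseline is a full two weeks, and every visit is inside its window.

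**Average.** Assumption: all 49 pairs (b, c) are equally likely.

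| Undosed days | Pairs |
|---|---|
| 0 | 40 |
| 1 | 5 |
| 2 | 3 |
| 3 | 1 |

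- Pairs affected: 9 of 49 (18%).
- Mean: (5 × 1 + 3 × 2 + 1 × 3)/49 = 14/49 = 0.29 day.
- Mean share of the collected window: when c is less than b the window is shorter than 14 days. The nine shares sum to 10/14 + 3/13 + 1/12 = 1.028, and 1.028/49 = 2.1%.

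**Effect on the definitive trial.** Assume the effect ends with the last capsule and events are spread evenly over days. The effect then shrinks by f = 0.021 on average. Required sample size scales with 1/effect², so the factor is 1/(1 − 0.021)² = 1.04. If the effect persists, f = 0 and the factor is 1.

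**Targets fixed on the calendar instead.** Count from study day 1, with Visits 2, 3 and 4 targeted at days 15, 29 and 43. Visit 2 on day 12 means capsules on nights 12 to 39. Visit 3 on day 32 means outcome days 32 to 45, with Visit 4 on day 46. Days 40 to 45 are undosed: 6 of 14 (43%). With Visit 1 on day 1, this leaves only 11 baseline days. Requiring a full 14-day baseline from a fixed Visit 1 brings the maximum back to 3. It returns to 6 only if Visit 1 is also three days early.

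**Supply needed.** Counted from the first dose, the latest Visit 4 is day 32 and the night before is day 31: 31 capsules. On calendar targets, the longest gap from Visit 2 to Visit 4 is 46 − 12 = 34 days: 34 capsules. In either case, dosing to the night before Visit 4 leaves 0 undosed outcome days.

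**The case against.** The strongest reply is that this hardly matters, and much of that stands.

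- **Pharmacology.** The capsule is extended-release and taken at bedtime, so the first day counted as undosed is still within 24 hours of the last dose until that evening. The count is therefore somewhat generous. This does not cover the second and third days.
- **Persistence.** The rationale in section 2 is recovery of awareness by blocking a propagating mechanism, and the design allows a two-week lead-in. Neither suggests an effect that vanishes overnight. Section 2 also cites increased sweating under propranolol in a clamp study, which might need drug on board. The documents do not settle how long the effect lasts.
- **Scale.** Section 10 describes the pilot analyses as mainly descriptive. With 12 subjects (10 degrees of freedom, assuming normal data), the 95% interval for the variance alone moves a planned sample size by a factor of 0.49 to 3.08. A 4% shift is small beside that.
- **Direction.** Both arms follow the same schedule, so this is dilution, not a source of false positives.

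A reader might infer that 6 of 14 days is the operative figure, from Visits 2 and 3 moving in opposite directions. The documents do not support that as the main reading. Section 4.1 ties the second assessment to drug start. The 6-day case needs calendar-fixed targets, Visit 4 three days late as well, and either an early Visit 1 or a baseline cut below the two weeks required by sections 4.1 and 6.1. Even with calendar targets it is 1 of 343 offset triples.

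A reader might likewise reach an average loss of 8.2% and a 19% larger sample size. Those figures combine calendar targets with a window that runs past Visit 4, whereas section 9.10.1 closes it there.

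**Conclusion.** The point holds at modest size. Following the stated rules exactly can place up to 3 of 14 outcome days (21%) after the last capsule, and no rule prevents or handles this. The average is 0.29 day, or 2.1% of the window, if offsets are uniform; the documents give no actual distribution. The resulting dilution is about 2%, or roughly 4% on a definitive-trial sample size, if the effect ends with dosing. It is zero if the effect persists. Six days remains only an outer bound, possible because footnote 2 leaves the anchor undefined. This is a cheap improvement and not a threat to the pilot's conclusions.

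**What to change.** **Preferred.**

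- In section 8, footnote 2, count the Visit 3 and Visit 4 targets from the first dose.
- In section 6.2.2, dispense 31 capsules (34 if targets stay fixed on the calendar).
- In sections 6.1 and 6.3, continue blinded dosing in both arms until the night before Visit 4.

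This removes every undosed outcome day and also keeps the Visit 4 questionnaires next to the last dose. The cost is 3 more capsules per subject (36 for 12 subjects), at most 3 more days on 80 mg or placebo, a few sentences and matching consent text. No visits or CGM days are added. The trade-off is that treatment length follows Visit 4, at 25 to 31 days instead of a nominal 28.

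**Alternative with no extra drug.** Set the Visit 3 window at −3 to 0 days from first dose + 14, and end the assessment after 14 days. The window then always closes by capsule 28. The cost is a tighter, one-sided Visit 3 window and a lead-in of 11 to 14 days.

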9 STUDY PROCEDURES

Detailed descriptions of subject evaluations required for this protocol are described in this section. These evaluations will be performed during the indicated visits/weeks of the study as described in the Study Calendar and in this section.

All data collected are to be recorded on source documents and entered into the appropriate CRF page.

The PI is responsible for maintaining a record of all subjects pre-screened, screened, and enrolled into the study. All subjects must provide written informed consent before the performance of any study procedures.

9.1 Pre-screening

The principal investigator (PI) will work with the University of Utah Enterprise Data Warehouse (EDW) and generate a list of potential candidates with based on the elements of inclusion/exclusion criteria (e.g. type 1 diabetes, age, recent hemoglobin A1C, etc) on the Human Subject Recruitment tool. Human Subject Recruitment tool is a computer software managed by EDW for subject recruitment with a constantly updating database, and this tool has been utilized by clinical investigators at the University of Utah. PI will review of these candidates' medical charts for further candidate selection.

The list of potential candidates will then be used to recruit subjects in the following routes:

- 1) The primary care physicians or Endocrinologists with established clinical relationship with the potential candidates may discuss the research opportunity with the candidates, to obtain the permission of contact for interested candidates, and/or offer recruitment letters.
- 2) A recruitment letter may be offered to the potential candidates by the medical assistants of physicians with established clinical relationship with these candidates, with permissions of the physicians.
- 3) A recruitment letter sent via mail or myChart message to the potential candidates, and if no response is received in at least 7 days, a phone call may be generated to discuss the study.

Information about the current study will also be distributed to clinicians, mostly primary care physicians and endocrinologists, and referrals for the current study may be made by these physicians.

For interested candidates, we will proceed with further eligibility pre-screening through telephone discussions and mailing paper surveillance of Personal Medical History and Hypoglycemia Awareness Questionnaires. A copy of the consent form will also be mailed to the candidates to look over for at least 1 day before obtaining consent.

For each recruitment route, the candidate may opt-out request for no further contact to be made for this study.

Social Networking Sites: We may share recruitment materials on social network sites such as Facebook or Instagram that provide a brief announcement and description about the study, along with study contact information directing interested individuals to the University of Utah study coordinator(s). Current required IRB disclaimer language will be attached to all online recruitment materials utilized.* Recruitment language options are being attached as a word document to this study application. This recruitment language may be utilized in any of the above methods at various times throughout the recruitment period of the study. If the study team determines that IRB approved recruitment language requires a substantive change, we will submit that language to the IRB prior to use.

***IRB Disclaimer Language (required for all social media recruitment)**

The information posted on this site is consistent with the research reviewed and approved by the University of Utah Institutional Review Board (IRB). However, the IRB has not reviewed all material posted on this site. Contact the IRB if you have questions regarding your rights as a research participant. Also contact the IRB if you have questions, complaints, or concerns which you do not feel you can discuss with the investigator. The University of Utah IRB may be reached by phone at [contact] or by email at [contact].

9.2 Informed Consent

For candidates interested in the study, a copy of the consent form will be mailed to the candidates to look over for at least 1 day before obtaining consent.

The informed consent process is to be completed at the screening visit. Prior to conducting any study-related procedures, written informed consent must be obtained from the subject. The nature, scope and possible consequences, including risks and benefits, of the study will be explained to the subject by the PI or designee in accordance with the regulations and guidelines in the Statement of Compliance.

The recruiting investigators/coordinators will be trained to discuss the study with the potential participants only limited to the informed consent document, including that the potential participant will continue to receive the same medical care regardless whether he/she decide to participate in the study. The potential participant selection process will be independent of the potential participants' diabetes care provider.

To avoid the study compensation being an undue influence, we will not share compensation information during pre-screening telephone calls unless the subject asks or after they have verbally agreed that they would like to participate. We also will not disclose details in compensation before completion of consenting process.

As much time as needed will be used to allow adequate time to exchange information and questions during the recruitment. The subjects and the investigators should not feel rushed for the recruitment process.

9.3 Screening and Study Entrance Criteria

At Screening, each subject will be assessed for eligibility against the inclusion/exclusion criteria. Subjects who do not meet the study entrance criteria will not be allowed to enroll and participate in the study. The reason(s) for ineligibility will be documented in the subject research chart.

9.4 Demographics and Medical History

Subject information including gender, age, date of birth, race, ethnicity, diagnosis of T1DM, and other relevant past medical history will be collected during the screening period and recorded in the appropriate CRF.

9.5 Laboratory Variables

Hemoglobin A1C and pregnancy test will be performed as indicated on the Study Calendar. Hemoglobin A1C Analysis of laboratory samples will be performed with ARUP Laboratories ([name]) protocol and supplies or at ARUP Laboratories. Pregnancy test will be performed with Immunostics Inc. ([name]) protocol and material.

9.5.1 Hemoglobin A1C

Hemoglobin A1C: Hemoglobin A1C, blood

9.5.2 Pregnancy Testing

Urinary pregnancy test: Qualitative Beta-human chorionic gonadotropin, urine

9.5.3 Specimen Collection, Preparation, Storage and Shipping

Specimen collection, preparation, storage and shipping will be conducted as the standard based on ARUP laboratory and Immunostics Inc. protocol.

9.6 Physical Examination

Physical examination, including respiratory, cardiovascular, abdominal and others as indicated based on medical history, will be conducted at the screening visit. For the follow-up visits, focused physical examination will be conducted at discretion of PI/sub-investigator based on reported adverse events.

9.7 Vital Signs

Vital signs, including measurement of systolic and diastolic blood pressure, pulse, and heart rate are to be conducted.

9.8 Electrocardiogram

An ECG will be completed during the screening period to assess for cardiac conduction abnormalities.

9.9 Concurrent Medications

All prescription and non-prescription medications including pharmacologic doses of vitamins, herbal medicines, or other non-traditional medicines, taken from 4 weeks prior to the first dose of the studied medications (propranolol/placebo) through the last study visit will be documented and recorded in the CRF.

9.9.1 Prohibited Concurrent Medications

The following medications are prohibited during the study:

- Beta-blockers other than propranolol
- Naltrexone and other medications that have been proposed to have the potential in improving hypoglycemia awareness or preventing the development of impaired awareness of hypoglycemia

9.9.2 Prohibited Procedure

The use of un-blinded continuous glucose monitoring is prohibited during the study. Behavioral modifications or relaxation of glycemic control aiming to improve hypoglycemia awareness are prohibited.

9.10 Efficacy Measurements

9.10.1 Primary Objective Assessment

The primary objective assessment will be done through the determining the total and self-reported hypoglycemic events based on CGM data and hypoglycemia diary, respectively.

A single CGM hypoglycemic episode will be defined by any CGM readings < 70 mg/dL, followed by at least one reading ≥ 70 mg/dL from the Dexcom Professional Mobile CGM system. A subject's self-reported hypoglycemic episode will be defined by a hypoglycemic symptom record on the hypoglycemia diary with a confirmatory glucose value (glucometer value < 70 mg/dL, or CGM glucose value < 70 mg/dL if glucometer value is not available), or an incidental glucometer value < 70 mg/dL if no hypoglycemia symptom develops.

The Hypoglycemia Event Report includes the initial glucometer value and time and treatment time; the first and the most prominent symptom during the hypoglycemia episode; whether the episode requires outside help (severe hypoglycemia).

At the end of each hypoglycemia event report/CGM assessment (i.e., visits 2 and 4), CGM data will be downloaded into a secure system and exported into an Excel format, and Hypoglycemic Event Reports will be collected for analysis.

The primary objective to determine whether propranolol increases the recognition of hypoglycemic events will be determined by an increase in the ratio of self-reported hypoglycemic events over total (i.e. CGM) hypoglycemic events while subjects are in the intervention period treated with propranolol compared to placebo.

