1.2 Secondary Objectives

- To determine whether propranolol improves hypoglycemia awareness questionnaire scores;
- To establish if propranolol reduces hypoglycemia severity and duration;
- To assess if propranolol decreases in onset-to-diagnosis/treatment and diagnosis/treatment-to-recovery duration and total hypoglycemia/severe hypoglycemia frequency (total/day/night);
- To establish whether propranolol decreases fear of hypoglycemia; and
- To determine if propranolol decreases overall mean blood glucose value.

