2 BACKGROUND

Type 1 diabetes mellitus (T1DM) can lead to serious and devastating complications, including microvascular (retinopathy, neuropathy and nephropathy) and cardiovascular disease. Both diabetic microvascular and cardiovascular complications can be reduced with intensive insulin therapy and strict blood glucose control which target hemoglobin A1C to less than 7%. [1] However, tighter glycemic control correlates with a higher incidence of hypoglycemia and severe hypoglycemia. [2] Recurring exposure to hypoglycemia leads to an attenuated sympathoadrenal response to hypoglycemia (which is termed hypoglycemia-associated autonomic failure), and thus a loss or decrease in neurogenic hypoglycemic symptoms (i.e. impaired awareness of hypoglycemia). [3, 4] Impaired awareness of hypoglycemia is associated with a six-fold increased risk of severe hypoglycemia [5] and physician or patient-directed higher glycemic goals. Impaired awareness of hypoglycemia is therefore a major barrier in diabetes management, by precluding optimal glycemic control and realization of its full benefits. [3]

Several therapeutic strategies have been proposed to improve hypoglycemia awareness in T1DM patients. A temporal increase in glycemic goal only sustains hypoglycemia awareness recovery for a short-term. [6, 7] Islet transplantation is invasive, extremely expensive and requires life-long use of immunosuppressants. [8] A widely available and affordable treatment with sustained efficacy for improving hypoglycemia awareness is therefore in urgent need. Pharmaceutical agents targeting potential mechanisms that contribute to the development of impaired hypoglycemia awareness have been proposed, including beta-blockers, opioid receptor antagonists and selective serotonin uptake inhibitors (SSRIs). [4] However, none of these agents has been approved for the treatment of impaired hypoglycemia awareness.

In the current study, we will examine the clinical use of beta-blockers, specifically propranolol, for the treatment of impaired hypoglycemia awareness. Prior rodent studies suggest that norepinephrine levels in the ventromedial hypothalamus (VMH) increase during an *acute* bout of hypoglycemia and that the *acute* activation of the VMH beta-2 adrenergic receptors enhances the

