9.10.2 Secondary Objective Assessment

Data for the secondary objective assessments will be collected through hypoglycemia awareness questionnaires (Gold, Clark and Pedersen-Bjergaard) [25-27], CGM data, and Fear of Hypoglycemia Questionnaire [28]. The questionnaires will be completed by study subjects at the first, second and the last visit of the study.

The questionnaires and CGM data will be used to determine changes in hypoglycemia awareness, severity and duration of hypoglycemia, onset-to-diagnosis/treatment and diagnosis/treatment-to-recovery durations, fear of hypoglycemia, and overall mean blood glucose values in subjects during the intervention period treated with propranolol compared to placebo.

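### The primary ratio divides diary and meter reports by CGM episodes without pairing the two, so it can exceed 1 and is not the share of CGM episodes recognised

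*Combined protocol and SAP*

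**What the plan says.** Section 9.10.1 bases the primary assessment on "total and self-reported hypoglycemic events based on CGM data and hypoglycemia diary, respectively". The outcome is the "ratio of self-reported hypoglycemic events over total (i.e. CGM) hypoglycemic events", compared between propranolol and placebo. Section 10 repeats the ratio for the exact Wilcoxon test and adds no detail on how it is built.

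A CGM episode is any reading below 70 mg/dL followed by at least one reading at or above 70. A self-report enters the numerator by one of three routes:

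- a symptom record with a glucometer value below 70;
- a symptom record confirmed by a "CGM glucose value < 70 mg/dL if glucometer value is not available";
- without symptoms, "or an incidental glucometer value < 70 mg/dL if no hypoglycemia symptom develops".

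On timing, "The Hypoglycemia Event Report includes the initial glucometer value and time and treatment time", along with symptoms and any need for outside help. Section 9.10.2 also plans "onset-to-diagnosis/treatment and diagnosis/treatment-to-recovery durations". Neither section gives a window or rule for linking a report to a CGM episode.

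**The concern.** The plan equates total events with CGM events, so a reader will take the ratio as the fraction of real episodes that the subject noticed. That holds only if every numerator event is also a denominator event, and nothing in the plan ensures it. A meter low while CGM reads 70 or above, or during a sensor gap, adds to the numerator alone.

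Two parts of the plan already need a time match that is not defined: CGM confirmation of a symptom record, and the onset-to-diagnosis/treatment durations. Analysts who chose different windows would get different results from the same data.

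Unmatched reports also add variation unrelated to recognition. The ratio is both the tested primary outcome and an input to the power analysis for the definitive cross-over trial (sections 4.3 and 10), so the extra noise and the unclear scale would carry forward.

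A separate, lesser matter is that crediting symptom-free meter lows makes the ratio rise with the number of routine tests. Section 5.2, item 13, sets a minimum of four a day and no maximum.

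**Working it through.** The plan gives no power, effect size, SD, episode rate, episode length or unmatched rate, so there is no figure of its own to reproduce. From the documents come 12 subjects (section 4.3), two-week assessments (section 8) and at least four meter tests a day (section 5.2). Every other input below is an assumption.

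**1. Can the ratio exceed 1?** In two of the three numerator routes a meter value below 70 is enough and CGM is never consulted. Take 10 CGM episodes, 6 recognised by symptoms, 2 caught by a routine test, and 3 further meter lows while CGM stayed at or above 70.

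- As written: (6 + 2 + 3)/10 = 1.10.
- Matched, with incidental lows kept: (6 + 2)/10 = 0.80.
- Matched, symptomatic only: 6/10 = 0.60.

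**2. Expected value.** Let s be the probability that a CGM episode is recognised by symptoms, q the probability that an unrecognised one is caught by a routine test, and u the number of unmatched reports per CGM episode. The expected ratio is s + (1 − s)q + u. If q and u are equal in both arms, the expected difference is (1 − q)(s₁ − s₀). Here u cancels from the mean difference but still adds variance.

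**3. Noise from unmatched reports.** I simulated 60,000 null trials per case with 6 subjects per arm. Symptom recognition was beta (mean 0.30, SD 0.15) and tests per day normal (6, 2), floored at 4. CGM episodes were Poisson (15) with a minimum of 1, unmatched reports Poisson (u × episodes), and q = 1 − exp(−tests × minutes/1440).

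| Unmatched per 100 CGM episodes | 95% limit of absolute arm difference (30 / 60 min episodes) | At least one of 12 ratios above 1 (30 / 60 min) |
|---|---|---|
| 0 | 0.210 / 0.202 | 0 / 0 |
| 5 | 0.218 / 0.213 | 1.5% / 2.8% |
| 10 | 0.229 / 0.224 | 5.7% / 10.2% |
| 20 | 0.248 / 0.243 | 26.2% / 40.9% |

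A separately coded run agreed within simulation error. With about 5 CGM episodes per subject, the last column becomes 10.5% / 15.0%, 23.8% / 32.8% and 53.5% / 65.7% at 5, 10 and 20 per 100.

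Under a different set of assumptions (recognition 0.40 v 0.70, q = 0.17, mean 14 CGM episodes), power of the exact test at 6 v 6 was 0.43, 0.33 and 0.21 with means of 0, 1 and 3 unmatched reports per subject. With no true difference and equal rates in both arms, rejection stayed between 0.040 and 0.051 across all cases.

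**4. Incidental lows.** With k tests evenly spaced over 24 hours and episodes of D minutes, q = kD/1440. At k = 4:

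- D = 30: 120/1440 = 0.083
- D = 60: 240/1440 = 0.167
- D = 120: 480/1440 = 0.333

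With equal q in the arms, a true difference of 0.20 in symptom recognition reads 0.20 × (1 − q) = 0.183, 0.167 and 0.133.

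With unequal q the direction is open. For s = 0.40 v 0.70:

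- q of 0.17 on placebo and 0.33 on propranolol gives (0.70 + 0.30 × 0.33) − (0.40 + 0.60 × 0.17) = 0.799 − 0.502 = 0.297, almost no loss.
- The reverse gives 0.751 − 0.598 = 0.153, about half lost.
- With s = 0.40 in both arms, the same values give a spurious 0.60 × 0.16 = 0.096 in one direction or the other.

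**The case against.** **The incidental rule is deliberate.** Section 9.10.1 writes symptom-free meter lows into the definition, and the primary objective in section 1.1 is recognition of events, not of symptoms. Awareness has its own secondary objective, "To determine whether propranolol improves hypoglycemia awareness questionnaire scores". A reader might infer from section 2, which describes "a loss or decrease in neurogenic hypoglycemic symptoms (i.e. impaired awareness of hypoglycemia", that counting these lows is an error and that a symptomatic ratio should replace the primary measure. The documents do not support that. Replacement would change the endpoint and brings its own loss, because a low treated before symptoms appear would count as unrecognised. This objection stands, and only a sensitivity analysis is warranted.

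**Repeat reports.** It is tempting to add that several reports of one low would inflate the numerator. The Event Report is framed per episode and asks for the initial glucometer value, so this route is weak. A one-report limit is still worth stating.

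**The consequences may be small.** The rank test and the Hodges-Lehmann estimate do not need an outcome bounded at 1. Section 10 calls the feasibility analyses mainly descriptive, and at 5 to 10 unmatched reports per 100 the added noise is slight. All of this is fair, and the unmatched rates are assumed. It does not answer the main point: the rule as written yields a number that is not the share of total events recognised, and that number is tested and carried into the next trial's design.

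**Conclusion.** The concern about pairing holds on the text alone: the numerator need not be a subset of the denominator, and no section supplies a rule or window. How much this matters depends on an unmatched rate that the documents do not give. Over 5 to 20 per 100 CGM episodes, with about 15 episodes each and 6 subjects per arm, the null 95% limit rises from 0.20-0.21 to 0.21-0.25. At least one ratio exceeds 1 in about 2% to 41% of trials.

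The incidental-low point is secondary and conditional. It shrinks a difference in symptom recognition by about 8% to 33% for assumed episodes of 30 to 120 minutes at four tests a day, provided the catch rate is equal in both arms. If the rates differ, the effect can go either way, so a modest shrinkage cannot be taken as established.

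A reader might also infer that the definition favours propranolol or inflates type I error. Neither is shown. With equal testing and equal unmatched rates the test keeps its level, and nothing in the documents indicates that these rates differ by arm. The point should be fixed, and the fix is cheap.

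**What to change.** In section 9.10.1, before unblinding:

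- Define the numerator as CGM episodes during CGM wear that have a matching self-report, symptomatic or incidental as now counted. The denominator is all CGM episodes in the same wear time.
- Match on glucometer time, or on treatment time if there is no meter value, within a fixed window (for example 15 minutes, repeated at 30). Allow at most one report per episode.
- State how CGM readings that oscillate around 70 are merged into one episode, and how subjects with no CGM episodes are handled.
- Use the same pairing for the durations in section 9.10.2.
- Report meter-confirmed lows with no CGM episode by arm, with a sensitivity analysis that adds them to both numerator and denominator (in the example above, 11/13 = 0.85).
- Keep incidental lows in the primary ratio. Pre-specify the symptomatic-only matched ratio as a sensitivity analysis, and tabulate incidental lows and tests per day by arm.

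The cost is wording and some programming, since the Event Report already lists the times needed. The main downside is that meter-confirmed lows without a CGM episode leave the main ratio. Symptom-onset time is not a listed field, so the symptomatic-only ratio cannot fully separate a symptom that prompted a test from one noted after it.
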